7.1.1. ECG Changes

A participant who meets either of the bulleted criterion based on the average of triplicate ECG readings will be withdrawn from the study.

- QTcF > 500 msec.
- Change from baseline: QTcF >60 msec.

If a clinically significant finding is identified (including, but not limited to, changes from baseline in QTcF after enrollment), the investigator or qualified designee will determine if the participant can continue in the study and if any change in participant management is needed. This review of the ECG printed at the time of collection must be documented. Any new clinically relevant finding should be reported as an AE.

See the SoA for data to be collected at the time of intervention discontinuation and follow-up and for any further evaluations that need to be completed.

7.1.2. Potential Cases of Acute Kidney Injury

Abnormal values in SCr concurrent with presence or absence of increase in BUN that meet the criteria below, in the absence of other causes of kidney injury, are considered potential cases of acute kidney injury and should be considered important medical events.

An increase of $\geq 0.3 \text{ mg/dL}$ (or $\geq 26.5 \mu \text{mol/L}$) in SCr level relative to the participant's own baseline measurement should trigger another assessment of SCr as soon as practically feasible, preferably within 48 hours from awareness.

If the second assessment (after the first observations of $\geq 0.3 \text{ mg/dL}$ [or $\geq 26.5 \mu \text{mol/L}$] in SCr relative to the participant's own baseline measurement) is $\geq 0.4 \text{ mg/dL}$ (or $\geq 35.4 \mu \text{mol/L}$), the participant should be discontinued from the study and adequate, immediate, supportive measures taken to correct apparent acute kidney injury.

Participants should return to the investigator site and be evaluated as soon as possible, preferably within 48 hours from awareness of the second assessment confirming abnormal SCr result. This evaluation should include laboratory tests, detailed history, and physical

assessment. In addition to repeating SCr, laboratory tests should include serum BUN, serum creatine kinase, and serum electrolytes (including at a minimum potassium, sodium, phosphate/phosphorus, and calcium), in addition to urinary dipstick, urine microscopic examination, and urinary indices. All cases confirmed on repeat testing as meeting the laboratory criteria for acute kidney injury, with no other cause(s) of laboratory abnormalities identified, should be considered potential cases of drug-induced kidney injury irrespective of availability of all the results of the investigations performed to determine etiology of the abnormal SCr. If \geq 2 healthy participants in a given treatment arm are noted to have 2 consecutive SCr results of \geq 0.3 mg/dL (or \geq 26.5 µmol/L), an assessment of whether the finding may be considered an adverse drug reaction should be undertaken.

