6.5.2. Individual Stopping Rules

If an individual participant exceeds any of the following, the participant will be discontinued from the study and will enter early termination visit as per SoA:

- Any of the following values (to be confirmed at 24 hours $[\pm 8 \text{ hours window}]$):
 - ECG changes (as described in Section 7.1.1), potential acute kidney injury (as described in Section 7.1.2), and potential drug-induced liver injury (as described in Appendix 6);
 - Any laboratory values or clinically significant findings meeting criteria of CTCAE v5.0 Grade 3 or greater.
- Any SAE (irrespective of relatedness to study drug).
- Any adverse dermal findings that, at the discretion of the study team and investigator, indicate that dosing should be halted.
- Please refer to Section 7 for additional individual discontinuation criteria.

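### Protocol 7.1.2 writes the creatinine discontinuation threshold and the two-participant trigger as absolute values where rises from baseline are meant (low-severity wording correction)

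*Protocol*

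**What the plan says.** Protocol Section 7.1.2 has three creatinine steps.

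- **Repeat test.** An increase of at least 0.3 mg/dL (26.5 µmol/L) over the participant's own baseline "should trigger another assessment of SCr as soon as practically feasible, preferably within 48 hours from awareness".
- **Discontinuation.** The sentence on the second assessment first recalls the 0.3 mg/dL observation in a parenthesis and then gives the new cut-off: "in SCr relative to the participant's own baseline measurement) is" at least 0.4 mg/dL (35.4 µmol/L). If that is met, "the participant should be discontinued from the study and adequate, immediate, supportive measures taken to correct apparent acute kidney injury".
- **Arm-level trigger.** If two or more healthy participants in a treatment arm have two consecutive SCr results of at least 0.3 mg/dL (26.5 µmol/L), "an assessment of whether the finding may be considered an adverse drug reaction should be undertaken".

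Section 6.5.2 makes potential acute kidney injury, by cross-reference to 7.1.2, a reason for which "the participant will be discontinued from the study and will enter early termination visit as per SoA". The SAP contains no creatinine stopping rule. Its Section 3.1.2 assesses laboratory abnormalities against the sponsor's reporting standards, not against these thresholds.

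**The concern.** Only the first step says that the figure is a change. In the second, the reference to baseline belongs to the earlier observation and does not reach the 0.4 mg/dL cut-off. In the third there is none. As written, both are absolute concentrations.

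A confirmatory test should separate a sustained rise from one that has resolved, and an absolute cut-off of 0.4 mg/dL does not do that. The neighbouring ECG rule in 7.1.1 labels its QTcF change criterion explicitly as a change from baseline, so the omission here is out of line with the protocol's own drafting. This is an individual stopping rule in a first-in-human study, and its threshold should be right as written.

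**Working it through.** **Inputs.** The thresholds 0.3 mg/dL (26.5 µmol/L) and 0.4 mg/dL (35.4 µmol/L) are from Protocol 7.1.2. The documents give no creatinine range for participants, so baselines of 0.5, 0.7, 0.9 and 1.2 mg/dL are assumed for illustration. The creatinine molar mass of 113.12 g/mol is also an assumption.

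**Step 1: reproduce the protocol's figures.** µmol/L = mg/dL × 10,000 / 113.12 = mg/dL × 88.4.

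- 0.3 × 88.4 = 26.52, stated as 26.5.
- 0.4 × 88.4 = 35.36, stated as 35.4.

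Both pairs agree, so the numbers are sound and only the wording is at issue.

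**Step 2: discontinuation step.** Let b be the baseline and r the repeat value, in a participant who has already shown a first rise of at least 0.3 mg/dL.

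- Literal rule: stop if r ≥ 0.4.
- Intended rule: stop if r − b ≥ 0.4, that is, r ≥ b + 0.4.

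The two disagree when 0.4 ≤ r < b + 0.4.

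| Assumed b (mg/dL) | Literal: stop at | Intended: stop at | Rules disagree for r | Repeat back at baseline (r = b) |
|---|---|---|---|---|
| 0.5 | ≥0.4 | ≥0.9 | 0.4 to <0.9 | literal stop; intended no stop |
| 0.7 | ≥0.4 | ≥1.1 | 0.4 to <1.1 | literal stop; intended no stop |
| 0.9 | ≥0.4 | ≥1.3 | 0.4 to <1.3 | literal stop; intended no stop |
| 1.2 | ≥0.4 | ≥1.6 | 0.4 to <1.6 | literal stop; intended no stop |

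The last column does not depend on the chosen values. If b is 0.4 mg/dL or more and the repeat returns to b, then r = b ≥ 0.4 and the literal rule is met.

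**Step 3: arm-level trigger.** Read literally, a participant counts once two consecutive values are at least 0.3 mg/dL. No earlier rise is required. Safety laboratory tests are scheduled on Days 5, 7, 10 and 12 after dosing starts (Schedule of Activities), so consecutive results exist for anyone who stays in. On the assumption that participants' creatinine lies above 0.3 mg/dL, as in the range above, any two participants in an arm meet it with no change at all. The two vehicle participants of a cohort would be enough.

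**Step 4: direction of error.** Since b cannot be negative, r ≥ b + 0.4 implies r ≥ 0.4, and two rises of at least 0.3 imply two values of at least 0.3. Everyone caught by the intended rules is also caught by the literal ones, so the literal wording can only add stops or assessments.

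**The case against.** The best defence is that nobody would read the section literally. The paragraph is in shorthand throughout. Even the parenthesis describes the first observation without the word *increase*, and there it plainly means a rise. The next paragraph refers to "awareness of the second assessment confirming abnormal SCr result", which makes no sense if a value back at baseline counts as confirmation. The discontinuation step is also reached only after a genuine first rise of at least 0.3 mg/dL, so even the literal wording cannot stop a participant with stable creatinine. The arm-level trigger leads to an assessment and stops no dosing.

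All of this stands, and it is why the point is minor. It does not make the text correct: the operative sentence still states the wrong quantity.

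A reader might go further and infer that Section 6.5.2 leaves open whether a confirmed rise of 0.3 to below 0.4 mg/dL requires a stop. That section gives no figure, and 7.1.2 speaks generally of values "that meet the criteria below, in the absence of other causes of kidney injury, are considered potential cases of acute kidney injury" and of "All cases confirmed on repeat testing as meeting the laboratory criteria for acute kidney injury". The documents do not support this as a defect. Section 6.5.2 handles its ECG, kidney and liver criteria by the same ordinary cross-reference. The 0.4 mg/dL figure is the only creatinine value that 7.1.2 ties to discontinuation. The 0.3 mg/dL figure has its own uses, for the repeat test and the arm-level assessment. If a confirmed 0.3 already forced a stop, the separate 0.4 step would have nothing to do.

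**Conclusion.** The point holds as a wording error in two places in 7.1.2. Rises from the participant's own baseline are clearly intended; absolute values are written. Followed exactly, after a first rise of at least 0.3 mg/dL the repeat test could not clear a participant who had returned to any baseline of 0.4 mg/dL or more, and the arm-level assessment would be set off by essentially any two participants. Only the second of these consequences needs an assumption about usual creatinine values.

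Severity is low. The error leans towards unnecessary stops and assessments, and neither document ties an endpoint or analysis to these thresholds. Two stronger inferences are not supported. One is that a kidney injury could be missed, which Step 4 rules out. The other is that the wording has a calculable cost in withheld applications. An early stop would withhold the same applications whether it was right or wrong, and the documents give no frequency for a first rise of 0.3 mg/dL, so the effect of the wording itself cannot be sized.

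**What to change.** In Protocol 7.1.2:

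- For the second assessment, write: *shows an increase over that participant's baseline of ≥0.4 mg/dL (≥35.4 µmol/L)*.
- For the two-participant trigger, write: *2 consecutive SCr increases over own baseline of ≥0.3 mg/dL (≥26.5 µmol/L)*.

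This is two phrases. No threshold changes, no test, visit or participant is added, and neither Section 6.5.2 nor the SAP needs an edit.

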7.2. Participant Discontinuation/Withdrawal From the Study

A participant may withdraw from the study at any time at his/her own request, or may be withdrawn at any time at the discretion of the investigator. Reasons for discontinuation from the study include the following:

- Refused further study procedures;
- Lost to follow-up;
- Death;
- Study terminated by sponsor;
- Behavioral, compliance, or administrative reasons.

At the time of discontinuing from the study, if possible, an early discontinuation visit should be conducted. See the SoA for assessments to be collected at the time of study discontinuation and follow-up and for any further evaluations that need to be completed.

The early discontinuation visit applies only to participants who are enrolled/randomized and then are prematurely withdrawn from the study. Participants should be questioned regarding their reason for withdrawal.

The participant will be permanently discontinued from the study intervention and the study at that time.

If a participant withdraws from the study, he/she may request destruction of any remaining samples taken and not tested, and the investigator must document any such requests in the site study records and notify the sponsor accordingly.

If the participant withdraws from the study and also withdraws consent (see Section 7.2.1) for disclosure of future information, no further evaluations should be performed and no additional data should be collected. The sponsor may retain and continue to use any data collected before such withdrawal of consent.

When a participant withdraws from the study because of an SAE, the SAE must be recorded on the Case Report Form (CRF) and reported on the Clinical Trial (CT) SAE Report.

Lack of completion of all or any of the withdrawal/early termination procedures will not be viewed as protocol deviations so long as the participant's safety was preserved.

7.2.1. Withdrawal of Consent

Participants who request to discontinue receipt of study intervention will remain in the study and must continue to be followed for protocol-specified follow-up procedures. The only exception to this is when a participant specifically withdraws consent for any further contact with him or her or persons previously authorized by the participant to provide this information. Participants should notify the investigator in writing of the decision to withdraw consent from future follow-up, whenever possible. The withdrawal of consent should be explained in detail in the medical records by the investigator, as to whether the withdrawal is only from further receipt of study intervention or also from study procedures and/or posttreatment study follow-up, and entered on the appropriate CRF page. In the event that vital status (whether the participant is alive or dead) is being measured, publicly available information should be used to determine vital status only as appropriately directed in accordance with local law.

Participants who withdraw from the study for *non-safety reasons* may be replaced at the discretion of the investigator upon consultation with the sponsor.

7.3. Lost to Follow up

A participant will be considered lost to follow-up if he or she repeatedly fails to return for scheduled visits and is unable to be contacted by the study site.

The following actions must be taken if a participant fails to return to the clinic for a required study visit:

- The site must attempt to contact the participant and reschedule the missed visit as soon as possible. Counsel the participant on the importance of maintaining the assigned visit schedule and ascertain whether the participant wishes to and/or should continue in the study;
- Before a participant is deemed lost to follow-up, the investigator or designee must make every effort to regain contact with the participant (where possible, 3 telephone calls and, if necessary, a certified letter to the participant's last known mailing address or local equivalent methods). These contact attempts should be documented in the participant's medical record;
- Should the participant continue to be unreachable, he/she will be considered to have withdrawn from the study.

8. STUDY ASSESSMENTS AND PROCEDURES

The investigator (or an appropriate delegate at the investigator site) must obtain a signed and dated ICD before performing any study-specific procedures.

Study procedures and their timing are summarized in the SoA. Protocol waivers or exemptions are not allowed.

Safety issues should be discussed with the sponsor immediately upon occurrence or awareness to determine whether the participant should continue or discontinue study intervention.

Participants will be screened within 28 days prior to application of the study intervention to confirm that they meet the study population criteria. If the time between screening and dosing exceeds 28 days as a result of unexpected delays (eg, delayed drug shipment), then participants do not require rescreening if the laboratory results obtained prior to first dose administration meet eligibility criteria.

A participant who qualified for this protocol but did not enroll from an earlier cohort/group may be used in a subsequent cohort/group without rescreening, provided laboratory results obtained prior to the first dose administration meet eligibility criteria for this study. In addition, other clinical assessments or specimen collections, eg, banked biospecimens, may be used without repeat collection, as appropriate.

Immediate safety concerns should be discussed with the sponsor immediately upon occurrence or awareness to determine if the participant should continue or discontinue study intervention.

Adherence to the study design requirements, including those specified in the SoA, is essential and required for study conduct.

All screening evaluations must be completed and reviewed to confirm that potential participants meet all eligibility criteria. The investigator will maintain a screening log to record details of all participants screened and to confirm eligibility or record reasons for screening failure, as applicable.

Every effort should be made to ensure that protocol-required tests and procedures are completed as described. However, it is anticipated that from time to time there may be circumstances outside the control of the investigator that may make it unfeasible to perform the test. In these cases, the investigator must take all steps necessary to ensure the safety and well-being of the participant. When a protocol-required test cannot be performed, the investigator will document the reason for the missed test and any corrective and preventive actions that he or she has taken to ensure that required processes are adhered to as soon as possible. The study team must be informed of these incidents in a timely manner.

Safety/laboratory/analyte results that could unblind the study will not be reported to investigative sites or other blinded personnel until the study has been unblinded.

If an IV catheter is utilized for blood sample collections, ECGs and vital sign assessments (pulse rate and BP) should be collected prior to the insertion of the catheter.

For samples being collected and shipped, detailed collection, processing, storage, and shipment instructions and contact information will be provided to the investigator site prior to initiation of the study.

The total blood sampling volume for individual participants in this study is approximately 165 mL. The actual collection times of blood sampling may change. Additional blood samples may be taken for safety assessments at times specified by Pfizer, provided the total volume taken during the study does not exceed 550 mL during any period of 60 consecutive days.

To prepare for study participation, participants will be instructed on the information in the LifeStyle Considerations and Concomitant Therapy sections of the protocol.

8.1. Efficacy Assessments

Not Applicable.

8.2. Safety Assessments

Planned time points for all safety assessments are provided in the SoA. Unscheduled clinical laboratory measurements may be obtained at any time during the study to assess any perceived safety issues.

8.2.1. Physical Examinations

A complete physical examination will include, at a minimum, head, ears, eyes, nose, mouth, skin, heart and lung examinations, lymph nodes, and gastrointestinal, musculoskeletal, and neurological systems.

A brief physical examination will include, at a minimum, assessments of general appearance, the respiratory and cardiovascular systems, and participant-reported symptoms.

Physical examinations may be conducted by a physician, trained physician's assistant, or nurse practitioner as acceptable according to local regulation.

Height and weight will also be measured and recorded as per the SoA. For measuring weight, a scale with appropriate range and resolution is used and must be placed on a stable, flat surface. Participants must remove shoes, bulky layers of clothing, and jackets so that only light clothing remains. They must also remove the contents of their pockets and remain still during measurement of weight.

Physical examination findings collected during the study will be considered source data and will not be required to be reported, unless otherwise noted. Any untoward physical examination findings that are identified during the active collection period and meet the

definition of an AE or SAE (Appendix 3) must be reported according to the processes in Sections 8.3.1 to Section 8.3.3.

8.2.2. Vital Signs

Supine BP will be measured with the participant's arm supported at the level of the heart, and recorded to the nearest mm Hg after approximately 5 minutes of rest. The same arm (preferably the dominant arm) will be used throughout the study. Participants should be instructed not to speak during measurements.

The same properly sized and calibrated BP cuff will be used to measure BP each time. The use of an automated device for measuring BP and pulse rate is acceptable; however, when done manually, pulse rate will be measured in the brachial/radial artery for at least 30 seconds. When the timing of these measurements coincides with a blood collection, BP and pulse rate should be obtained prior to the nominal time of the blood collection.

Additional collection times, or changes to collection times, of BP and pulse rate will be permitted, as necessary, to ensure appropriate collection of safety data.

8.2.3. Electrocardiograms

12-Lead ECGs should be collected at times specified in the SoA section of this protocol using an ECG machine that automatically calculates the heart rate and measures PR, QT, and QTcF intervals and QRS complex. All scheduled ECGs should be performed after the participant has rested quietly for at least 10 minutes in a supine position.

Triplicate 12-lead ECGs will be obtained approximately 2 to 4 minutes apart; the average of the triplicate ECG measurements collected before dose administration on Day 1 will serve as each participant's time-controlled baseline QTcF value.

To ensure safety of the participants, a qualified individual at the investigator site will make comparisons to baseline measurements. Additional ECG monitoring will occur if a) the mean value from the triplicate measurements for any postdose QTcF interval is increased by \geq 30 msec from the baseline and is >450 msec; or b) an absolute QTcF value is \geq 500 msec for any scheduled ECG. If either of these conditions occur, then a single ECG measurement must be repeated at least hourly until QTcF values from 2 successive ECGs fall below the threshold value that triggered the repeat measurement.

If a postdose QTcF interval remains \geq 30 msec from the baseline and is >450 msec; or b) an absolute QTc value is \geq 500 msec for any scheduled ECG for greater than 4 hours (or sooner, at the discretion of the investigator), or QTc intervals get progressively longer, the participant should undergo continuous ECG monitoring. A cardiologist should be consulted if QTc intervals do not return to less than the criterion listed above after 8 hours of monitoring (or sooner, at the discretion of the investigator).

In some cases, it may be appropriate to repeat abnormal ECGs to rule out improper lead placement as contributing to the ECG abnormality. It is important that leads be placed in the

same positions each time in order to achieve precise ECG recordings. If a machine-read QTcF value is prolonged, as defined above, repeat measurements may not be necessary if a qualified medical provider's interpretation determines that the QTcF values are in the acceptable range.

ECG values of potential clinical concern are listed in Appendix 7.

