- b. Participants will be discharged on D12, following completion of all scheduled procedures. Participants who may experience AEs or dermatological observations on D12 may be confined to the CRU at the discretion of the PI until AEs or dermatological observations are resolved and may be asked to return to the CRU at the discretion of the investigator, for follow-up contact. If unexpected reactions (eg, rash, hives) other than irritation reactions outlined in, Section 8.2.5 occur, the body surface area location must be recorded. Appearance of the reactions should be described.
- c. Participants will be scheduled for a follow-up phone call on D41±3 days. Additional follow-up contacts may be scheduled at investigator's discretion, including follow-ups to monitor open AEs based on emerging safety data.
- d. Participants will be admitted at least 12 hours prior to dosing.
- e. Medical history will be collected at screening and updated on D-1 only.
- f. Complete physical examination will be conducted at screening or on D-1 only; otherwise brief physical examination is envisioned for findings during previous or new/open AEs, at the discretion of the PI.
- g. Check for exposure to COVID-19 positive participants as per standard CRU protocol.
- h. Singlet measure at screening and early termination only. Triplicate measures at all other times approximately 2-4 minutes apart; ECGs will be measured on D1 and D10 as specified in Table 2; ECGs will be measured at pre-AM application on D2, D5 and D7, on D11 at approximately 24H post last application and on D12 prior to discharge.
- i. Vitals will be collected at screening and early termination; vitals should be measured on D1 and D10 as specified in Table 2; vitals should be collected at pre- AM application on D2, D5 and D7; vital signs will be collected on D11 at approximately 24H post last application and D12 prior to discharge.

Table 1. Schedule of Activities from Screening to End of Study

Visit Identifier ^a	Screening		In patient									Follow-Up Contact/EOS	Early Termination/ Discontinuation	
Days Relative to Day 1	≤-28	Day -1	1	2	3-4	5	6	7	8-9	10	11	12 ^b	41±3°	

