3. OBJECTIVES AND ENDPOINTS

4. STUDY DESIGN

4.1. Overall Design

C4711001 is an investigator- and participant-blinded, interventional, randomized, vehiclecontrolled, Phase 1 study to evaluate the safety, and local and systemic tolerability and pharmacokinetics of maximum feasible formulation of topical JAK inhibitors, PF-07295324 (0.12%) and PF-07259955 (2%) in healthy adult participants.

This study will enroll healthy adult participants in \leq 4 cohorts: 2 planned cohorts and 2 optional cohorts. Approximately 6 participants will be enrolled in each cohort, randomized as 4 active:2 vehicle. Cohort 1 and the optional Cohort 3 will be assigned to PF-07295324/vehicle, administered topically as an ointment. Cohort 2 will be assigned to PF-07259955/vehicle administered topically as a cream. PF-07295324 or PF-0725995 may be studied in optional Cohort 4.

Participants will be enrolled in the optional cohorts in a sequential design to the respective planned cohort, as shown in Section 1.2. Planned cohorts assigned to different interventions may progress simultaneously. Similarly, optional cohorts assigned to different interventions may progress simultaneously (Section 1.2).

Healthy adult participants will be screened for eligibility criteria within 28 days prior to the administration of the first dose in each part of the study. Participants enrolled in 1 cohort of this study will not be allowed to enroll in any other cohorts of the study. Participants enrolled in each of the cohorts will be discharged following completion of all scheduled assessments as specified in the SoA.

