9.1. Statistical Hypotheses

No statistical hypotheses will be tested in this study.

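### The QTcF trigger for additional ECGs does not cover every participant who meets the >60 msec withdrawal criterion, the confirmation ECG has no stated format, and the early-termination ECG is a single tracing

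*Protocol*

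**What the plan says.** **Monitoring trigger.** Protocol Section 8.2.3 provides: "Additional ECG monitoring will occur if a) the mean value from the triplicate measurements for any postdose QTcF interval is increased by" 30 msec or more "from the baseline and is >450 msec". The alternative trigger is an absolute QTcF of at least 500 msec. Either one leads to hourly single ECGs until two successive values fall below the threshold. Continuous monitoring and a cardiology consultation may follow.

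**Withdrawal criterion.** Protocol Section 7.1.1 works on the average of triplicate readings. Either of two findings suffices: QTcF above 500 msec, or "Change from baseline: QTcF >60 msec". The second has no absolute floor.

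**Confirmation.** Protocol Section 6.5.2 lists the Section 7.1.1 ECG changes among values to be confirmed at 24 hours (±8 hours). After that, "the participant will be discontinued from the study and will enter early termination visit as per SoA". It does not state the format of the confirming ECG, and Section 7.1.1 does not mention a confirmation.

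**Format by visit.** Note h to Table 1 of the Schedule of Activities (SoA) reads: "Singlet measure at screening and early termination only". ECGs at all other times are triplicate, including the Day 1 predose baseline.

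**Analysis.** SAP Section 6.1.1.4 takes the maximum QTcF increase over all postdose measurements and labels an increase above 60 msec Severe.

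**The concern.** The protocol treats a QTcF change above 60 msec as enough to end participation. The paragraph that orders closer ECG follow-up reaches such a change only if the absolute value also passes 450 msec. Participants with low baselines fall between the two rules. Exclusion criterion 20 gives only an upper QTcF limit (450 msec), so such baselines are eligible.

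Two further points are left open. A site cannot tell from Section 7.1.1 alone that withdrawal awaits a confirming reading, nor from Section 6.5.2 whether that reading must be triplicate. And the ECG taken as a participant leaves early is on a different measurement basis from the baseline it is compared with. ECG findings are part of the primary safety endpoint of a first-in-human study, so these rules should fit together.

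**Working it through.** The plan states no figure to reproduce: "No statistical hypotheses will be tested in this study". The check compares the two rules and then the precision of the two ECG formats.

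**1. Where the rules diverge.** Let B be baseline and P the postdose triplicate mean, in msec.
- Withdrawal (7.1.1): P > 500, or P − B > 60.
- Trigger (8.2.3): (P − B ≥ 30 and P > 450), or P ≥ 500.
- Any P > 500 also satisfies P ≥ 500, so the absolute limb of the withdrawal rule leaves no gap.
- On the change limb, P − B > 60 already implies P − B ≥ 30, so the trigger fails only when P ≤ 450. The gap is B + 60 < P ≤ 450, which requires B < 390.

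| Baseline | Postdose values (whole msec) meeting withdrawal but not the trigger |
|---|---|
| 360 | 421–450 |
| 370 | 431–450 |
| 380 | 441–450 |
| 389 | 450 only |

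Example: 380 to 445 is +65, which meets the withdrawal criterion and neither trigger. On an integer grid with baselines from 340 to 450, each B below 390 contributes 390 − B gap values. The total is 50 + 49 + … + 1 = 50 × 51 / 2 = 1,275 pairs. All have B ≤ 389 and P ≤ 450. The lower end of 340 is an arbitrary choice for the enumeration.

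**2. Who could be in the gap.** The documents give no baseline distribution. Assume a normal distribution with SD 15 to 20 msec, truncated at 450. Let f be the share below 390; the chance that at least one of a cohort's four active participants is below 390 is 1 − (1 − f)^4.

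| Assumed mean | f | At least 1 of 4 |
|---|---|---|
| 390 | 50% | 94% |
| 400 | 25–31% | 69–77% |
| 410 | 9–16% | 32–51% |
| 420 | 2–7% | 9–26% |

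This is the chance of having a baseline from which the gap can be reached, not the chance of a rise above 60 msec.

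**3. What happens before early termination.** The confirmation window is 24 ± 8, or 16 to 32 hours after the first reading. On Days 1 and 10, Table 2 already schedules triplicates at 0, 1, 4, 8, 12 and 24 hours. Readings on Days 2, 5 and 7 would be confirmed about a day later, on Days 3, 6 and 8, where Table 1 has no ECG. The confirming ECG is then unscheduled. Note h suggests triplicate, but neither section says so.

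**4. Single versus triplicate at early termination.** Let each tracing have independent error SD s. The SD of the change from a triplicate baseline is:
- single tracing: s × √(1 + 1/3) = 1.155s
- triplicate: s × √(1/3 + 1/3) = 0.816s
- ratio: 1.155 / 0.816 = 1.41, or 41% larger.

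Tracings 2 to 4 minutes apart share session-level variation. If between-session variance equals within-session variance (an assumption), the ratio is √[(2 + 4/3) / (4/3 + 4/3)] = √(3.33 / 2.67) = 1.12, or 12% larger.

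**The case against.** A monitoring trigger and a stopping rule may have different thresholds, and a site can obey both. That stands: the rules are misaligned, not mutually exclusive. It does not explain why a change sufficient for withdrawal falls outside the additional-monitoring paragraph, and the protocol gives no reason.

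Four stronger readings are tempting, and the documents do not support them:
- **A reader might infer that early termination is always the next ECG.** Section 6.5.2 places a confirmation first, and Table 2 schedules further triplicates on Days 1 and 10. A participant back under the criterion at confirmation does not meet the confirmed stopping rule.
- **A reader might infer that the trigger gap is why recovery lacks triplicate evidence.** The triggered repeats are themselves single ECGs, so participants above 450 msec could also leave without a triplicate recovery reading. These are two separate matters.
- **A reader might infer that a +65 msec change to 445 gets less follow-up than a +31 msec change to 451.** The second gets hourly single tracings, which may be dispensed with on a qualified overread. The first gets confirmation, discontinuation, an early-termination visit and investigator review.
- **A reader might infer that the single tracing distorts the SAP category of those withdrawn for QTcF.** Anyone above 60 msec on a triplicate mean is already in the top increase category. The precision point concerns people who terminate early for other reasons.

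There are also backstops. Section 7.1.1 requires investigator review and AE reporting of new clinically relevant findings. Appendix 7 lists a rise of 60 msec or more as a possible AE, AEs are followed to resolution or stabilization, and unplanned visits are allowed. Section 8.2.3 also calls for continuous monitoring if QTc lengthens progressively, though seeing that requires repeat readings. These narrow the gap, but they rest on judgement or leave the ECG format open.

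Finally, the study is small ("Approximately 6 participants will be enrolled in each cohort, randomized as 4 active:2 vehicle") and the risk table in Section 2.3.1 lists no QT risk. That argues for modest severity.

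**Conclusion.** The point holds in limited form and is worth correcting, though it is not critical. For baselines below 390 msec, a participant can meet the Section 7.1.1 change criterion at 450 msec or less without any repeat ECGs being mandated by the Section 8.2.3 thresholds, either while confirmation is pending or once the change is confirmed. This follows from the stated thresholds alone. How many participants could be affected depends on an assumed baseline distribution: the chance that at least one of four active participants has such a baseline runs from 9% to 94%. A rise above 60 msec may itself be rare.

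Sections 6.5.2 and 7.1.1 also differ on whether withdrawal awaits confirmation, and neither states the format of the confirming ECG.

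The single early-termination tracing is a separate, smaller measurement weakness. For participants who stop early for other reasons, a noisier value enters the maximum-increase categories beside triplicate means. The excess SD is at most 41% under independent errors, and 12% in the correlated example.

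**What to change.** 1. Reconcile Protocol Sections 6.5.2, 7.1.1 and 8.2.3 and SoA note h, so that it is explicit what ECG follow-up applies to a participant who meets a Section 7.1.1 criterion, before and after confirmation. The medical team decides the thresholds and monitoring steps; this review proposes none.
2. State in Sections 6.5.2 and 7.1.1 whether the 24-hour confirmation applies to the ECG criteria and whether it is triplicate. Provide for it in the SoA on days with no scheduled ECG.
3. As a separate measurement improvement, put the early-termination ECG on the same triplicate basis as baseline in Table 1 and note h.

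The cost of items 1 and 2 is a few sentences in a protocol amendment plus the medical team's review. Item 3 costs two extra tracings, about 4 to 8 minutes, for each participant who terminates early, and removes the format difference from the SAP's maximum-increase categories.
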